5.6.2. Descriptive Analysis of Secondary Efficacy Endpoints

All analyses for the secondary efficacy endpoints are descriptive and all p-values are nominal.

5.6.2.1. Descriptive Analysis of Secondary Virologic Efficacy Endpoints

The time-weighted average daily change from baseline in viral load (\log_{10} copies/mL) from day 1 to all post-baseline visit timepoints will be descriptively analyzed similar to primary virologic analysis for patients by serostatus in mFAS, by baseline viral load ($\leq 10^5$ vs $> 10^5$ copies/mL and $\leq 10^6$ vs $> 10^6$ copies/mL) (with serostatus added to the ANCOVA model as a factor) in the mFAS, and overall mFAS (with serostatus added to the ANCOVA model as a factor).

To assess the time course of treatment effect in viral load, the change from baseline in viral load (\log_{10} copies/mL) at each visit for seronegative mFAS and overall mFAS will be analyzed using

a mixed-effect model for repeated measures (MMRM) with terms for baseline viral load, type of background standard-of-care, treatment, visit, treatment by baseline interaction, baseline by visit interaction, and treatment-by-visit interaction. Within-patient errors will be modeled with an unstructured covariance matrix. The least squares means estimates for the mean at each visit and mean change from baseline to each visit as well as the difference of these estimates between each anti-S mAb treatment arm and placebo will be provided along with the corresponding standard error, p-value, and associated 95% confidence interval. The percentage change from baseline in viral load in raw scale at each visit will be back-transformed from the \log_{10} -transformed viral load and presented along with the change from baseline in viral load (\log_{10} copies/mL). The analysis will be performed for patients by serostatus in the mFAS, by baseline viral load ($\leq 10^5$ vs $> 10^5$ copies/mL and $\leq 10^6$ vs $> 10^6$ copies/mL) (with serostatus added to the MMRM model as a factor) in the mFAS, and in overall mFAS (with serostatus added to the MMRM model as a factor).

5.6.2.2. Descriptive Analysis of Secondary Clinical Efficacy Endpoints

All clinical endpoints based on proportions (defined in Section 4.5.2.3) will be analyzed using similar methods as for the primary clinical efficacy endpoint described in Section 5.6.1.2. The analysis will be performed for patients by baseline viral load ($\leq 10^6$ vs $> 10^6$ copies/mL) in the mFAS, by serostatus in the mFAS, and in overall mFAS.

All clinical endpoints based on time-to-event (defined in Section 4.5.2.4) will be estimated using the Kaplan-Meier method and comparisons between treatment groups will be made using the stratified log-rank test with the type of background standard-of-care as stratification factor. P-values will be compared with 0.05 (two-sided).

The log-rank “observed minus expected” statistic (and its variance) will be used to calculate the one-step estimate of the event rate ratio and confidence interval for each pairwise comparison versus placebo group (Peto 1977) [2].

As sensitivity analysis, the hazard ratio and its 95% CI will be estimated by the Cox proportional-hazards regression model with terms for treatment group, and type of background standard-of-care. P values from the stratified log-rank test will be reported. Hazard ratio (HR) < 1 will imply reduction of hazard of REGN10933+REGN10987 versus placebo. Estimates of median times along with 25th and 75th percentiles (if median and quartiles are reached) and associated two-sided 95% CI will be reported using the Kaplan-Meier method.

Landmark analysis starting from day 6 will be performed using similar Cox proportional-hazard model on the cumulative incidence of death or mechanical ventilation and cumulative incidence of death. The patients with corresponding events occurring before day 6 and patients who drop out early from study before day 6 will be excluded from the analysis (Dafni, U. 2011) [3]. The analysis will be performed for patients by baseline viral load ($\leq 10^6$ vs $> 10^6$ copies/mL) in mFAS (with baseline serostatus added to the stratified log-rank test and the Cox model as a factor), by serostatus in mFAS, and overall mFAS (with baseline serostatus added to the stratified log-rank test and the Cox model as a factor).

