11.2.3. Phase 3 (Cohort 1)

Initial estimation

The sample size for phase 3 was initially estimated to be 1350 patients (150 patients per arm across 3 treatment arms in 3 cohorts). Based on the new endpoint of death or mechanical ventilation, the sample size for phase 3 has been re-estimated to be 2505 patients in each of cohort 1 and cohort 1A.

The study was planned to continue enrolling additional patients seamlessly into the phase 3 portion of the study, until an adaptation decision on the dose(s), primary endpoint and final sample size for phase 3 is made based on the phase 2 data analysis. A total sample size of approximately 5010 patients was estimated for the phase 3 portion of the study (2505 per cohort, 835 per arm across 3 treatment arms in 2 cohorts). For cohort 1, a total of 241 events (estimated sample size of 2505 patients [835 patients per arm]) would have been needed to provide 90% power at $\alpha=0.05$ (2-sided) using a log-rank test to detect a risk reduction of 35.8% (ie, HR=0.642) in the cumulative incidence of patients who died or went on mechanical ventilation, assuming a 12.5% cumulative incidence rate in the placebo group by day 29.

Final sample size

Finalization of the sample size and patient population for phase 3 was planned to be subject to change and would be determined after review of phase 2 data. However, enrollment of patients into the study was terminated prematurely by the Sponsor on 09 April 2021 because of extremely slow enrollment in the months preceding the decision. The sample size of phase 3 was not re-estimated.

Approximately 2252 patients were randomized in the study, which includes 60 patients in phase 1 cohort 1, 629 in phase 2 cohort 1, 755 in planned phase 3 cohort 1, 609 in phase 2 cohort 1A, 164 in phase 2 cohort 2 and 35 in phase 2 cohort 3.

Assuming the proportion of patients who died or went on mechanical ventilation from day 1 to day 29 in placebo group is 13.1% which is same as the blinded proportion in the Seronegative mFAS patients of the pooled phase 3 cohort 1 and phase 2 cohort 1A and alpha is 0.05 2-sided, the minimal significant difference in relative risk reduction between the REGN10933+REGN10987 2.4g and 8.0g combined dose group and placebo group is 29.0%, 41.2%, and 36.6% for overall mFAS, Seronegative mFAS, and High Viral Load mFAS patients, respectively.

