- Other therapies (immune-based therapies, both antiviral and immune-based therapies, or no COVID-19-specific treatment)

Phase 2/3

In phase 2/3, patients were randomized in a 1:1:1 allocation ratio to one of the following treatment groups:

- Co-administered REGN10933+REGN10987 combination therapy 2.4 g (1.2 g of REGN10933 plus 1.2 g of REGN10987) IV single dose
- Co-administered REGN10933+REGN10987 combination therapy 8.0 g (4.0 g of REGN10933 plus 4.0 g of REGN10987) IV single dose
- Placebo IV single dose

Randomization in phase 2/3 was stratified by country and type of background standard-of-care being administered for COVID-19 at randomization as follows:

- Antiviral therapies (remdesivir or other)
- Non-antiviral therapies (immune-based therapies, both antiviral and immune-based therapies, or no COVID-19-specific treatment)

The enrollment into Cohorts 2 and 3 were paused based on a recommendation from the IDMC (initial IDMC recommendation on 30 October 2020).

Most of the patients in the study were enrolled in the United States. Other countries where patients were enrolled in the study include Romania, Brazil, Chile, Mexico, and Moldova.

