5.6. Analyses of Efficacy Endpoints

The efficacy analyses will be performed for the following subjects on all efficacy endpoints, separately. The comparisons in all efficacy endpoints will be performed between the the REGN10933+REGN10987 2.4g and 8.0g combined dose group and placebo group as well as between each treatment group and placebo group.

- Pooled phase 3 Cohort 1 and phase 2 cohort 1A subjects
- Phase 3 Cohort 1 subjects (ie, subjects randomized after 01DEC2020 in Cohort 1)
- Phase 2 cohort 1A subjects

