5.6.3. Adjustment for Multiple Comparisons

Multiplicity Considerations

The following multiplicity adjustment approach, a hierarchical procedure, will be used to control the overall Type-1 error rate at 0.05 for the primary virologic and clinical outcome endpoints in comparison between the combined doses of REGN10933+REGN10987 treatment group and placebo group in the pooled phase 3 cohort 1 and phase 2 cohort 1A patients. Each hypothesis will be formally tested only if the preceding one is significant at the 2-sided 0.05 significance level. The hierarchical testing order is shown in [Table 9](#).

Table 9: Hierarchical testing order

Type	Description	Testing Order
Primary virologic outcome	Time-weighted average change from baseline viral load in NP sample through day 7 in seronegative mFAS for comparing the combined doses of REGN10933+REGN10987 versus placebo	1
Primary clinical outcome	Proportion of patients who died or went on mechanical ventilation from day 6 to day 29 in High Viral Load mFAS for comparing the combined doses of REGN10933+REGN10987 versus placebo	2
	Proportion of patients who died or went on mechanical ventilation from day 6 to day 29 in Seronegative mFAS for comparing the combined doses of REGN10933+REGN10987 versus placebo	3
	Proportion of patients who died or went on mechanical ventilation from day 6 to day 29 in overall mFAS for comparing the combined doses of REGN10933+REGN10987 versus placebo	4
	Proportion of patients who died or went on mechanical ventilation from day 1 to day 29 in High Viral Load mFAS for comparing the combined doses of REGN10933+REGN10987 versus placebo	5
	Proportion of patients who died or went on mechanical ventilation from day 1 to day 29 in Seronegative mFAS for comparing the combined doses of REGN10933+REGN10987 versus placebo	6
	Proportion of patients who died or went on mechanical ventilation from day 1 to day 29 in overall mFAS for comparing the combined doses of REGN10933+REGN10987 versus placebo	7

All other analyses for virologic and clinical endpoints will be reported descriptively for each individual cohort and for pairwise comparison of each REGN10933+REGN10987 dose group (2.4 g IV or 8.0 g IV) versus placebo.

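### For death and ventilation in the 2:1 combined-dose comparison, the SAP's main rate ratio (one-step Peto) modestly overstates a true benefit, while the Cox hazard ratio is only a sensitivity analysis

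*SAP*

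**What the plan says.** SAP 5.6.2.2 analyses the time-to-event endpoints by Kaplan-Meier and a log-rank test stratified by background standard-of-care. For the size of the effect, the observed-minus-expected result of that test "will be used to calculate the one-step estimate of the event rate ratio and confidence interval for each pairwise comparison versus placebo group". The next paragraph begins "As sensitivity analysis, the hazard ratio and its 95% CI will be estimated by the Cox proportional-hazards regression model", with background standard-of-care as a model term. The day-6 landmark analysis of death, and of death or ventilation, uses a Cox model instead.

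SAP 5.6 requires every efficacy endpoint to be compared between the "combined dose group and placebo group as well as between each treatment group and placebo group". SAP 2.1 gives the allocation: "In phase 2/3, patients were randomized in a 1:1:1 allocation ratio to one of the following treatment groups". Combined doses versus placebo is therefore 2:1, and each dose versus placebo is 1:1.

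SAP 5.6.3 uses the word pairwise more narrowly, for "pairwise comparison of each REGN10933+REGN10987 dose group (2.4 g IV or 8.0 g IV) versus placebo". SAP 5.6.2 makes all secondary efficacy analyses descriptive, with nominal p-values.

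**The concern.** The one-step ratio, exp[(O−E)/V], takes one step from a hazard ratio of 1. It is accurate near 1 and nearly so with equal groups. With two treated patients per control and a real effect, it departs from the hazard ratio. For an unfavourable event such as death, a true benefit looks larger than it is.

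These analyses are descriptive, so the estimate and interval are their main content. Two comparisons a reader will make are also affected. Combined-dose and single-dose ratios carry errors in opposite directions. The day-1 and day-6 analyses of the same endpoint use different main estimators.

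**Working it through.** **Inputs.** Allocation 1:1:1 (SAP 2.1). Effect size HR 0.642 with 241 events, 2505 patients, 835 per arm and 12.5% placebo incidence (Protocol 11.2.3, initial phase 3 estimate). Placebo risk of 13.1% for the final analysis (SAP 2.3). The plan gives no figure for the behaviour of the one-step ratio.

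**1. The plan's own log-rank figure.** Schoenfeld's formula is events = (1.960 + 1.282)² / [π(1−π)(ln HR)²], with π the treated share.
- π = 2/3: 10.507 / (0.2222 × 0.1964) = 240.8, so 241. This matches the Protocol.
- π = 1/2: 215, which does not match.
- Expected events with 835 placebo patients at 12.5% and 1670 active at 1 − 0.875^0.642 = 8.2% come to 241.6.

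The plan's log-rank arithmetic thus fits a 2:1 comparison.

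**2. Limit of the one-step ratio.** With few events and constant hazards, and total events proportional to T = π·HR + 1 − π:
- O − E is proportional to π·HR − π·T = π(1−π)(HR − 1)
- V is proportional to π(1−π)T
- so ln R = (HR − 1) / (π·HR + 1 − π), not ln HR.

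Example at 2:1 and HR 0.642: −0.358 / 0.7613 = −0.470, and exp(−0.470) = 0.625.

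| True HR | 2:1 limit | True / reported reduction | 1:1 limit |
|---|---|---|---|
| 1.00 | 1.000 | 0 / 0 | 1.000 |
| 0.80 | 0.794 | 20.0% / 20.6% | 0.801 |
| 0.642 | 0.625 | 35.8% / 37.5% | 0.647 |
| 0.50 | 0.472 | 50.0% / 52.8% | 0.513 |

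**3. Simulation at 2:1.** Death or ventilation, 13.1% placebo risk, constant hazards, whole-day event times, unstratified, 3000 trials per row. The size of 1200 is assumed because mFAS counts are not given. It lies in the range implied by the stated 29.0% minimal significant reduction for the overall mFAS. With risks of 13.1% and 9.3% and 2:1 groups, that figure needs about 1130 (pooled variance) to 1250 (unpooled) patients; 755 + 609 = 1364 were randomised.

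| True HR | One-step (geometric mean) | Cox | Bias in SE units | One-step 95% CI coverage |
|---|---|---|---|---|
| 1.00 | 0.997 | 1.002 | −0.02 | 95.2% |
| 0.80 | 0.791 | 0.801 | −0.06 | 93.4% |
| 0.642 | 0.623 | 0.643 | −0.15 | 93.3% |
| 0.50 | 0.469 | 0.499 | −0.31 | 92.0% |

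A second simulation with 400 placebo and 800 active patients gave one-step coverage of 93.1% (HR 0.642) and 91.8% (HR 0.50), against 95.0% and 94.8% for Cox. With 600 patients, one-step ratios were 0.619 and 0.469, with coverage of 92.5% and 92.7%.

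**4. Single doses (1:1), same endpoint.** One-step ratios were 0.636–0.647 at HR 0.642 and 0.509–0.513 at HR 0.50, with coverage of 94.7–96.6%. If both doses had a true HR of 0.50, each would tend to 0.51 and the pooled group to 0.47, so the pool would look better than both parts.

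**5. Time to discharge (2:1).** The event is favourable. With placebo discharge assumed at 80–90%, a true ratio of 1.2 gave 1.19–1.20 and 1.5 gave 1.475–1.488. Here the benefit is slightly understated.

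**The case against.** The strongest reply is that nothing formal depends on this ratio. The endpoints are secondary and descriptive. The primary clinical endpoint is a proportion, tested by CMH or Fisher with a Farrington-Manning relative risk, and no step of the hierarchy in SAP 5.6.3 uses the one-step ratio. The log-rank p-value does not change, and the Cox result will be reported anyway. All of this stands, and it makes the point minor.

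It can also be argued that the pairwise wording in SAP 5.6.2.2 covers single doses only, as in SAP 5.6.3, where the one-step ratio is nearly unbiased. That reading is possible. But SAP 5.6 requires the combined comparison on all efficacy endpoints, so SAP 5.6.2.2 would then name no main ratio for it. Either reading needs an edit.

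Stronger conclusions are tempting, and the documents do not support them:
- **That all time-to-event results favour the drug.** Time to discharge at 2:1 leans the other way, and the landmark analysis already uses Cox.
- **That Cox is unbiased.** It is consistent under proportional hazards. SAP 1.1 expects clinical impact only after several days of viral suppression. With such a delay there is no single hazard ratio from day 1, and both estimators give only an average effect.
- **That a larger sampling spread is a second defect.** It is the same distortion: the slope of the limit on the log scale at HR 0.642 is 0.642 / 0.761² = 1.11.
- **That 0.642 is the effect planned for the final analysis.** It belongs to the initial phase 3 estimate and serves here only as a reference value.

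**Conclusion.** The point holds in a limited form. It concerns death, mechanical ventilation and their composite, in the combined-dose comparison with placebo, analysed from day 1. There the SAP's main ratio overstates a true benefit by about 0.6, 1.7 and 2.8 percentage points of relative reduction at hazard ratios of 0.80, 0.642 and 0.50, and its 95% interval covers about 92–93%. The bias disappears at the null.

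The sizes rest on constant proportional hazards, low event rates, 13.1% placebo risk and assumed analysis-set sizes. A reader might infer that the trial's conclusions or its error control are at risk; they are not. This is an improvement to the reporting of secondary estimates.

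**What to change.** In SAP 5.6.2.2:
- Make the Cox hazard ratio and 95% CI the main ratio estimate, with background standard-of-care as a model term and serostatus where the SAP already adds it. This also matches the day-6 landmark analysis.
- Keep the stratified log-rank p-value.
- Move the one-step ratio to sensitivity.
- State that the pairwise comparisons include the combined dose group as well as each dose.

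Both analyses are already planned, so the cost is a few sentences and no new data or programming. The small downside is that, if the treatment effect is delayed, the Cox ratio needs the same caution as the one-step ratio: it is an average over follow-up.

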5.6.3. Adjustment for Multiple Comparisons

Multiplicity Considerations

The following multiplicity adjustment approach, a hierarchical procedure, will be used to control the overall Type-1 error rate at 0.05 for the primary virologic and clinical outcome endpoints in comparison between the combined doses of REGN10933+REGN10987 treatment group and placebo group in the pooled phase 3 cohort 1 and phase 2 cohort 1A patients. Each hypothesis will be formally tested only if the preceding one is significant at the 2-sided 0.05 significance level. The hierarchical testing order is shown in [Table 9](#).

Table 9: Hierarchical testing order

Type	Description	Testing Order
Primary virologic outcome	Time-weighted average change from baseline viral load in NP sample through day 7 in seronegative mFAS for comparing the combined doses of REGN10933+REGN10987 versus placebo	1
Primary clinical outcome	Proportion of patients who died or went on mechanical ventilation from day 6 to day 29 in High Viral Load mFAS for comparing the combined doses of REGN10933+REGN10987 versus placebo	2
	Proportion of patients who died or went on mechanical ventilation from day 6 to day 29 in Seronegative mFAS for comparing the combined doses of REGN10933+REGN10987 versus placebo	3
	Proportion of patients who died or went on mechanical ventilation from day 6 to day 29 in overall mFAS for comparing the combined doses of REGN10933+REGN10987 versus placebo	4
	Proportion of patients who died or went on mechanical ventilation from day 1 to day 29 in High Viral Load mFAS for comparing the combined doses of REGN10933+REGN10987 versus placebo	5
	Proportion of patients who died or went on mechanical ventilation from day 1 to day 29 in Seronegative mFAS for comparing the combined doses of REGN10933+REGN10987 versus placebo	6
	Proportion of patients who died or went on mechanical ventilation from day 1 to day 29 in overall mFAS for comparing the combined doses of REGN10933+REGN10987 versus placebo	7

All other analyses for virologic and clinical endpoints will be reported descriptively for each individual cohort and for pairwise comparison of each REGN10933+REGN10987 dose group (2.4 g IV or 8.0 g IV) versus placebo.

5.6.4. Analysis of Exploratory Endpoints

The change and percentage change in NLR, D-dimer, ferritin, CRP, and LDH will be summarized at each visit through day 29 using descriptive statistics for mFAS and FAS.

The proportion of patients with treatment failure having mutations in the gene encoding the SARS-CoV-2 S protein through day 29 will be analyzed in separate report.

5.7. Analysis of Safety Data

The analysis of safety data will be performed for cohort 1 in combined phases 1, 2 and 3, phase 2 cohorts 1A, 2 and 3, separately in the FAS population.

In this study, only targeted treatment-emergent adverse events will be recorded:

- All phases: Treatment-emergent adverse events of special interest (AESIs)
 - Grade ≥ 2 hypersensitivity
 - Grade ≥ 2 infusion-related reactions
- All phases: Treatment-emergent serious adverse events (SAEs)
- All phases: TEAEs (Grade 3 or Grade 4 only)

The safety analysis will be based on the reported SAEs and AESIs and other safety information (clinical laboratory evaluations and vital signs).

Thresholds for Potential Clinically Significant Values (PCSV) in laboratory variables and vital signs are defined in Section [10.3](#).

The summary of safety results will be presented for each treatment group.

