4.2. Secondary Endpoints

Pooled Phase 3 (Cohort 1) and Phase 2 (Cohort 1A)

Clinical

- Proportion of patients who went on mechanical ventilation by day 29
- Proportion of patients who died from day 6 to day 29 and from day 1 to day 29
- Proportion of patients who were discharged by day 29
- Proportion of patients who died or were readmitted to hospital over time
Note: Readmission to hospital will be based on investigator report.
- Cumulative incidence of death over time (ie, overall survival)
- Cumulative incidence of mechanical ventilation over time
- Cumulative incidence of death or mechanical ventilation over time
- Time to discharge

Safety and Tolerability

- Proportion of patients with treatment-emergent SAEs through end of study
- Proportion of patients with infusion-related reactions (grade ≥ 2) through day 4
- Proportion of patients with hypersensitivity reactions (grade ≥ 2) through day 29

Phase 1/2 (Cohort 1)***Clinical Efficacy***

The key secondary endpoint is death or mechanical ventilation.

Other secondary endpoints include:

Virologic Efficacy

- Time-weighted average change from baseline in viral load (\log_{10} copies/mL) from day 1 to day 7, as measured by quantitative reverse transcription polymerase chain reaction (RT-qPCR) in nasopharyngeal (NP) swab samples

Note: Time-weighted average of change from baseline in viral load from day 1 to day 7 will be calculated for each patient using the trapezoidal rule as the area under the curve for change from baseline at each time point divided by the time interval for the observation period.

- Time-weighted average change from baseline in viral load (\log_{10} copies/mL) from day 1 to day 11, as measured by RT-qPCR in NP swab samples
- Time-weighted average change from baseline in viral load (\log_{10} copies/mL) from day 1 to each post-baseline timepoint until day 29, as measured by RT-qPCR in NP swab samples
- Change from baseline in viral load at each post-baseline timepoint through day 29, as measured by RT-qPCR in NP swab samples
- Time to sustained negative RT-qPCR (negative RT-qPCR with no subsequent) positive

Clinical Efficacy

- All-cause death
- Mechanical ventilation
- Proportion of patients who died or went on mechanical ventilation by day 29
- Proportion of patients who died by day 29
- Proportion of patients who went on mechanical ventilation by day 29
- Time to discharge

PK/ADA

- Concentrations of REGN10987 and REGN10933 in serum and corresponding PK parameters

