- Immunogenicity, as measured by ADA and (in phase 2 and phase 3 only) NAb to REGN10933 and REGN10987

Phase 3 (Cohort 1) and Phase 2 (Cohort 1A), Separately

The secondary endpoints include:

Virologic Efficacy

Endpoint	Timepoint	Population
Time-weighted average change from baseline viral load in NP sample	Through day 7	mFAS
Time-weighted average change from baseline viral load in NP sample	Through day 7	Baseline Viral load categories ($>10^5$, $>10^6$ copies/mL) mFAS
Time-weighted average change from baseline viral load in NP sample	Through day 11	Seronegative mFAS
Time-weighted average change from baseline viral load in NP sample	Through day 11	mFAS
Time-weighted average change from baseline viral load in NP sample	Through day 11	Baseline Viral load categories ($>10^5$, $>10^6$ copies/mL) mFAS
Time-weighted average change from baseline, change from baseline, and percent change from baseline in viral load in NP sample	Through each post-baseline timepoint until day 29	1. Seronegative mFAS, 2. Baseline Viral load categories ($>10^5$, $>10^6$ copies/mL) mFAS, 3. mFAS

Clinical Efficacy

- Proportion of patients who went on mechanical ventilation by day 29 (as applicable)
- Proportion of patients who died from day 6 to day 29 and from day 1 to day 29
- Proportion of patients who were discharged by day 29
- Proportion of patients who died or were readmitted to hospital over time
Note: Readmission to hospital will be based on investigator report.
- Cumulative incidence of death over time (ie, overall survival)
- Cumulative incidence of mechanical ventilation over time (as applicable)
- Cumulative incidence of death or mechanical ventilation over time (as applicable)
- Time to discharge

Safety and Tolerability

- Proportion of patients with treatment-emergent SAEs through end of study
- Proportion of patients with infusion-related reactions (grade ≥ 2) through day 4
- Proportion of patients with hypersensitivity reactions (grade ≥ 2) through day 29

PK/ADA

- Concentrations of REGN10987 and REGN10933 in serum and corresponding PK parameters
- Immunogenicity, as measured by ADAs and NAbs to REGN10933 and REGN10987

Phase 2 (Cohort 2 and Cohort 3)***PK/ADA***

- Concentrations of REGN10987 and REGN10933 in serum and corresponding PK parameters
- Immunogenicity, as measured by ADAs and NAbs to REGN10933 and REGN10987

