1.2.2. Secondary Objectives

Pooled Phase 3 Cohort 1 and Phase 2 Cohort 1A

The secondary objectives are:

- To evaluate additional indicators of clinical efficacy of REGN10933+REGN10987 compared to placebo
- To evaluate the safety and tolerability of REGN10933+REGN10987 compared to placebo

Phase 2 (Cohort 1A)

The secondary objectives are:

- To evaluate the virologic efficacy of REGN10933+REGN10987 compared to placebo in reducing viral load of SARS-CoV-2
- To evaluate the clinical efficacy of REGN10933+REGN10987 compared to placebo, as measured by death or mechanical ventilation
- To evaluate the safety and tolerability of REGN10933+REGN10987 compared to placebo
- To characterize the concentrations of REGN10933 and REGN10987 in serum over time
- To assess the immunogenicity of REGN10933 and REGN10987

Phase 2 (Cohort 2 and Cohort 3)

The secondary objectives are:

- To characterize the concentrations of REGN10933 and REGN10987 in serum over time
- To assess the immunogenicity of REGN10933 and REGN10987

Phase 3 (Cohort 1)

The secondary objectives are:

- To evaluate the virologic efficacy of REGN10933+REGN10987 compared to placebo in reducing viral load of SARS-CoV-2
- To evaluate the clinical efficacy of REGN10933+REGN10987 compared to placebo, as measured by death or mechanical ventilation
- To evaluate additional indicators of clinical efficacy of REGN10933+REGN10987 compared to placebo
- To evaluate the safety and tolerability of REGN10933+REGN10987 compared to placebo

Phase 1/2/3 (Cohort 1)

The secondary objectives are:

- To evaluate the safety and tolerability of REGN10933+REGN10987 compared to placebo
- To characterize the concentrations of REGN10933 and REGN10987 in serum over time
- To assess the immunogenicity of REGN10933 and REGN10987

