5.7.1. Adverse Events

Summaries that include frequencies and proportions of patients reporting AEs will include the PTs and the SOCs.

An overview of adverse events will be provided by treatment group and for combined dose groups of R10933+R10987, including:

- Total number of TEAEs, SAEs, Total number of AESIs, Serious AESIs, Grade 3 or 4 TEAEs, as well as
- The number and percentage of patients with
 - any TEAE, any SAE, any AESI, any serious AESI, any grade 3 or grade 4 TEAE, any fatal TEAEs, any TEAEs leading to withdrawal from the study, any TEAEs leading to study infusion discontinuation, and any TEAEs leading to study infusion interruption.

Summaries of SAEs and AESIs by treatment group and for combined R10933+R10987 doses will include number (n) and percentage (%) of patients with at least :

- Treatment-emergent AE by SOC and PT
- Treatment-emergent AE by SOC and PT and CTCAE grade

- Treatment-emergent AE related to study treatment by SOC and PT
- Treatment-emergent SAE by SOC and PT
- Treatment-emergent AESIs presented by SOC and PT
- Treatment-emergent grade 3 or 4 AEs presented by SOC and PT

Counts will be provided according to treatment group for each PT within each SOC. Percentages will be calculated using the number of patients from the FAS in each treatment group.

Primary SOCs will be sorted according to decreasing order of frequency in combined treatment group. Within each primary SOC, PTs will be sorted by decreasing frequency in combined treatment group.

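### Safety objectives and endpoints are set for the pooled phase 3 cohort 1 + phase 2 cohort 1A patients and for phase 3 cohort 1 alone, but no safety summary is planned for either set

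*SAP*

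**What the plan says.** **Objectives.** Protocol 2.2 and SAP 1.2.2 list the same secondary objective, "To evaluate the safety and tolerability of REGN10933+REGN10987 compared to placebo", as separate entries for the pooled set, phase 3 cohort 1, phase 2 cohort 1A, and cohort 1 across phases 1/2/3.

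**Endpoints.** For the pooled set, Protocol 4.2 names three: "Proportion of patients with treatment-emergent SAEs through end of study", "Proportion of patients with infusion-related reactions (grade ≥ 2) through day 4" and "Proportion of patients with hypersensitivity reactions (grade ≥ 2) through day 29". It repeats all three under the heading "Phase 3 (Cohort 1) and Phase 2 (Cohort 1A), Separately".

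**Planned analysis.** SAP 5.7 states that safety will be "performed for cohort 1 in combined phases 1, 2 and 3, phase 2 cohorts 1A, 2 and 3, separately in the FAS population". Protocol 11.4.10 and the Synopsis use the same grouping, and SAP 1.1 and the overview in Protocol 11 list the same four groups. The pooled set and phase 3 cohort 1 alone are named as analysis groups only for efficacy (Protocol 11.4.6, SAP 5.6).

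**Reporting of adverse events of special interest (AESIs).** The overview in SAP 5.7.1 counts patients with any AESI. The detailed table is "Treatment-emergent AESIs presented by SOC and PT".

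**The concern.** The protocol promises safety results for two sets of patients, and its own statistical section, followed by the SAP, plans none for them. One of the two is the population in which the primary virologic and clinical hypotheses are tested. A reader of the study report would find efficacy in the pooled cohorts, and safety in a different grouping that overlaps them only in part. Two stated secondary safety objectives would have no result.

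A smaller gap lies in the layout. Infusion-related reactions and hypersensitivity reactions are separate endpoints, and Protocol 3.3.2 treats such reactions as the important identified risk. An any-AESI line merges them. A table by system organ class and preferred term does not guarantee a patient count for either one.

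**Working it through.** This is a consistency check, so the main step is to set the sets with a stated safety aim against the sets with a planned summary. Counts are the randomized numbers in SAP 2.3 and Protocol 7.1; counts for the full analysis set (FAS) are not given.

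| Set | Randomized | Safety objective | Safety endpoints in Protocol 4.2 | Planned safety summary |
|---|---|---|---|---|
| Pooled phase 3 cohort 1 + phase 2 cohort 1A | 755 + 609 = 1364 | secondary | three | none |
| Phase 3 cohort 1 | 755 | secondary | three | none |
| Phase 2 cohort 1A | 609 | secondary | three | yes |
| Cohort 1, phases 1/2/3 | 60 + 629 + 755 = 1444 | secondary | none under that heading | yes |
| Phase 2 cohort 2 | 164 | exploratory | none | yes |
| Phase 2 cohort 3 | 35 | exploratory | none | yes |

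**Coverage.** The stated counts give 60 + 629 + 755 + 609 + 164 + 35 = 2252, which reproduces the plan's total. The four planned safety groups give 1444 + 609 + 164 + 35 = 2252, so every randomized patient belongs to one of them.

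**Overlap.** Of the 1444 in the combined cohort 1 group, 60 + 629 = 689 are phase 1/2 patients outside the primary efficacy population: 689/1444 = 47.7%. The 755 phase 3 patients are 52.3% of that group and 755/1364 = 55.4% of the pooled set.

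**Can the missing results be rebuilt?** The pooled result needs phase 3 cohort 1 plus cohort 1A. The cohort 1A table exists, but phase 3 cohort 1 is never shown apart from phase 1/2. Subtracting the December 2020 phase 1/2 results would not recover it, because SAP 1.1 says that more safety data on those patients were collected after that lock.

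**Follow-up.** SAP 2.4.1 sets end of study at day 169 for phase 1 and day 57 for phases 2 and 3. In the combined group, the proportion with a serious event to end of study therefore mixes two observation periods. The longer one applies to 60/1444 = 4.2% of the group. Since allocation was 1:1:1 in every phase, this mainly affects the meaning of the absolute proportion and not the balance between arms.

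**Reaction types.** Protocol 10.2.3.1 and SAP 4.6.1 build the day 4 and day 29 limits into the event definitions, and SAP 4.6.2 restricts AESIs to these two types at grade 2 or higher. What SAP 5.7.1 lacks is a row for each type.

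**The case against.** The grouping is deliberate. Protocol 11 and SAP 1.1 explain that phase 1/2 patients are included because their safety data continued to accrue after the December 2020 lock, and Protocol 6.1.1 calls for analysis by cohort. Pooling was adopted for the primary analyses because of the reduced sample size, a reason with less force for cohort 1 safety, where 1444 patients are available. The SAP also follows the protocol's statistical section, so the conflict begins inside the protocol, and the objectives and endpoints could be trimmed to match. All of this stands. It justifies keeping the combined cohort 1 table, but it does not explain why the two sets with stated endpoints have no summary. The Synopsis line allowing subgroup analyses of safety as needed commits to neither set.

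Three stronger readings are tempting, and the documents do not support them.

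- A reader might infer that the planned grouping loses precision on rare reactions. It does not for cohort 1. Taking two-thirds of randomized patients as active, the combined group has about 963, and with zero events the one-sided 95% upper bound is 1 − 0.05^(1/963) = 0.31%. The pooled set, with about 909 active, gives 1 − 0.05^(1/909) = 0.33%.
- A reader might infer that the day 4 and day 29 windows cannot be applied. They can, because they are part of the event definitions.
- A reader might infer that benefit and harm cannot be compared at all in the pooled set. Death, mechanical ventilation, and death or readmission are analysed there against placebo (Protocol 4.2, SAP 5.6), and cohort 1A has its own full safety summary.

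**Conclusion.** The inconsistency is real and can be read directly from current text. If the plan is followed as written, three secondary safety endpoints go unreported for the pooled set (1364 randomized) and for phase 3 cohort 1 (755 randomized), and they cannot be recovered from the planned tables. The separate row for each reaction type is a minor but related omission.

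The defect is a missing summary, not missing data. The case rests on the mismatch between populations and on endpoints left without a result; it does not rest on precision. The sizes are randomized counts, and the FAS counts may be lower. The match that the fix achieves is also approximate: the added tables would cover the FAS of the pooled cohorts, while primary efficacy is tested in the overall, seronegative and high viral load subsets of the modified FAS. The change should be made, because it is specific and cheap and it settles a conflict between Protocol 4.2 and Protocol 11.4.10.

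**What to change.** In SAP 1.1 and 5.7, and in Protocol 11.4.10, add FAS safety summaries for (i) pooled phase 3 cohort 1 + phase 2 cohort 1A and (ii) phase 3 cohort 1. Present each by dose, for the combined doses, and for placebo. In SAP 5.7.1, add separate rows for treatment-emergent serious events, grade 2 or higher infusion-related reactions and grade 2 or higher hypersensitivity reactions, using the existing definitions. Align the group lists in the Synopsis and in the overview of Protocol 11. Keep all the existing tables.

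The cost is wording plus a few extra runs of existing table programs; no new data are needed. If the sponsor prefers not to add the summaries, the unmatched objectives and endpoints in Protocol 2.2 and 4.2 and SAP 1.2.2 should be removed with a stated reason. That would be consistent, but it would leave the primary efficacy population without a matching safety summary.
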